7.2.2. Unified Huntington's Disease Rating Scale

The UHDRS comprises 7 subscales with separate scoring for each part:

- Part I is an assessment of motor function. Part I includes 31 items with a 5-point ordinal scale ranging from 0 to 4 with the highest score indicating inability to perform the motor task. The “Diagnosis Confidence Level” is also collected as a portion of the UHDRS Motor Assessment.
- Part II is an assessment of cognitive function and includes 3 items with higher scores indicating better cognitive performance. The 3 items include a Verbal Fluency Test, SDMT, and Stroop Interference Test. In the Verbal Fluency Test, subjects are asked to enumerate either words beginning with a given letter within a limited amount of time (phonological fluency) or words within a given category, such as animals (semantic fluency). The SDMT is a symbol substitution neuropsychological test that examines a person’s attention and speed of processing. This test requires a person to substitute geometric symbols for numbers while scanning a response key. Oculomotor scanning, working memory, motor persistence, and visuomotor coordination are also required in order to score higher on the test. In order to prevent a learning effect from confounding the result of the SDMT, 3 different versions of the test will be administered at different timepoints for each subject. The Stroop Interference Test assesses the ability to selectively attenuate to specific items on the test, either word name or word color, when the 2 are interfering variables.
- Part III is a behavioral assessment. The PBA-s will be substituted for this behavioral assessment in this study.
- Part IV is a measure of functional capacity. Huntington’s Disease Functional Capacity Scale is reported as the TFC, which has a total of 25 yes or no questions assessing the TFC of the individual. A score of 1 is given to all yes replies.
- Part V is a measure of independence. The IS is measured on a scale from 10 to 100 with higher scores indicating better functioning.
- Part VI is a measure of functional capacity. Functional Capacity is measured using 5 items with a 3- or 4-point ordinal scale ranging from 0 to 2 or 0 to 3 with the highest score indicating higher functional capacity.
- Part VII is the clinical summary. An examination summary is performed by the examiner to take into account all aspects of the UHDRS.

7.2.3. Problem Behavior Assessment (Short Form)

The short form of the Problem Behavior Assessment is a semi-structured clinical interview that measures the occurrence and severity of 11 different behavioral symptoms in subjects with HD.

7.2.4. Opal Wearable Device Assessments

It has been noted in previous HD studies that bradykinesia, hypokinesia, gait speed, cadence, and increase in stride time are associated with HD decline. In order to assess changes in gait, balance, and postural sway, Opal wearable devices will be worn by the subject during 3, on-site

assessments: TUG in 3 m walkway, 2-minute walk distance, and a postural sway test. Each test will be conducted twice: once with a concurrent cognitive interference task and once without.

7.2.5. Functional Rating Scale

The FuRST 2.0 is a standardized HD-specific 24-item patient-reported outcome measure specifically designed to assess functional ability in pre-manifest and early-manifest HD.

8. ASSESSMENT OF SAFETY

8.1. Safety Parameters

The following have been defined as parameters regarding safety and tolerability:

- Abnormalities in vital signs
- Abnormalities in ECG parameters
- Abnormalities in clinical laboratory tests
- NfL levels in plasma and CSF
- Changes in C-SSRS scores
- TEAEs up to EOS
- TEAEs leading to premature discontinuation of study drug
- Treatment-emergent serious adverse events (SAEs) up to EOS
- Abnormalities in physical examination

8.1.1. Demographic/Medical History

Demographic data and medical history will be collected at the times indicated in the Schedule of Assessments ([Table 4](#)).

8.1.2. Vital Signs

Supine blood pressure, supine pulse rate, respiration rate, body temperature, and oxygen saturation will be assessed at the timepoints indicated in the Schedule of Assessments ([Table 4](#)). Vital signs may also be performed at other times if judged to be clinically appropriate or if the ongoing review of the data suggests a more detailed assessment of vital signs is required.

All measurements will be performed singly and repeated once if outside the relevant clinical reference range. Subjects must be supine for at least 5 minutes before blood pressure and pulse rate measurements.

8.1.3. Weight and Height

Body weight and height will be measured at the timepoints indicated in the Schedule of Assessments ([Table 4](#)).

8.1.4. Physical Examination

A complete physical examination will be performed at the timepoints specified in the Schedule of Assessments ([Table 4](#)). A complete physical examination includes general appearance, head, eyes, ears, nose, mouth, throat, thyroid, chest and lungs, abdomen, extremities, neuromuscular system, skin, and lymph nodes.

8.1.6. *Electrocardiogram*

Subjects will be in a supine position for approximately 5 minutes prior to ECG measurements. Measurements will be taken at the times indicated in the Schedule of Assessments ([Table 4](#)) and will be classified as normal/abnormal. In case of a classification as “abnormal,” the abnormality will be described and its relevance in terms of clinical significance documented. The ECGs will be performed in triplicate.

8.1.8. *Laboratory Assessments*

A summary of clinical laboratory tests to be performed is presented in [Table 5](#), with the timing of assessments as indicated in the Schedule of Assessments ([Table 4](#)). Clinically significant laboratory abnormalities which require clinical intervention or further investigation must be reported by the investigator as an AE or SAE as appropriate (Section [8.2.3](#)).

Safety blood samples will be taken under fasted conditions at Baseline. All other safety laboratory assessments are not required to be taken under fasted conditions. As a rule, the blood samples will be taken from the subject by puncture of a vein in the cubital or the antebrachial region. The samples will be sent to a central laboratory in accordance with specifications.

8.1.9. *Neurofilament Light Chain Levels*

The levels of NfL, a biomarker of neuronal injury, will be assessed in plasma and CSF as indicated in [Table 4](#).

Table 5: Summary of Clinical Laboratory Tests

Hematology	Chemistry	Urinalysis ^a	Others	CSF
Hemoglobin	Urea	Urobilinogen	Pregnancy test ^c	NfL
Hematocrit	Creatinine	Nitrite	FSH ^d	WBC ^e
RBC count	Glucose	pH	Serology (HIV, hepatitis B and hepatitis C) ^a	RBC ^e
Platelet count	Sodium	Glucose	Coagulation (PT [sec], PT [INR], aPTT)	Protein ^e
Mean corpuscular volume	Potassium	Albumin	Urine drug screen ^a	Glucose ^e
Mean corpuscular hemoglobin	ALT	Erythrocytes	Plasma NfL	
WBC count	AST	Leukocytes		
WBC differential	GGT	Ketones		
Neutrophils	Bilirubin (total, direct and indirect)	Microscopy ^b		
Band neutrophils	ALP	Specific gravity		
Eosinophils	Albumin	Bilirubin		
Monocytes	Cholesterol (total)			
Basophils	LDL			
Lymphocytes	HDL			
	Triglycerides			
	LDH			
	Bicarbonate			
	Calcium			
	Chloride			
	Total protein			
	Uric acid			

Abbreviations: ALP, alkaline phosphatase; ALT, alkaline aminotransferase; aPTT, activated partial thromboplastin time; AST, aspartate aminotransferase; CSF, cerebrospinal fluid; FSH, follicle-stimulating hormone; GGT, gamma-glutamyltransferase; HDL, high-density lipoprotein; INR, international normalized ratio; LDH, lactate dehydrogenase; LDL, low-density lipoprotein; NfL, neurofilament light chain; PT, prothrombin time; RBC, red blood cell; WBC, white blood cell

^a Only during Screening.

^b Only if urine dipstick is positive and marked as at least ‘++’ for erythrocytes/leucocytes and albumin.

^c Serum pregnancy testing at Screening and Baseline; at other timepoints urine pregnancy testing is acceptable. For months when no in-person visit is scheduled, a home pregnancy test will be taken by the subject and reported to the investigator.

^d Required of postmenopausal females only during Screening.

^e Assessment of CSF WBC, RBC, protein, and glucose will be performed by local laboratories.

8.1.10. Columbia Suicide Severity Rating Scale

The C-SSRS is a measure used to identify and assess individuals at risk for suicide. Questions are phrased for use in an interview format but can be completed as a self-report measure if necessary. The C-SSRS measures 4 constructs: suicidal ideation, the intensity of ideation, suicidal behavior, and lethality. It includes “stem questions,” which, if endorsed, prompt additional follow-up questions to obtain more information.

The C-SSRS suicidal ideation construct comprises 5 categories, all of which maintain binary responses (yes/no) to indicate a presence or absence of ideation. The 5 categories included in the C-SSRS ideation construct are as follows:

Category 1 – Wish to be Dead;

Category 2 – Non-specific Active Suicidal Thoughts;

Category 3 – Active Suicidal Ideation with Any Methods (Not Plan) without Intent to Act;

Category 4 – Active Suicidal Ideation with Some Intent to Act, without Specific Plan;

Category 5 – Active Suicidal Ideation with Specific Plan and Intent

The C-SSRS intensity of ideation construct is measured by evaluating on a 1 to 5 ordinal scale the following parameters: frequency, duration, controllability, deterrents, reason for and ideation.

A yes/no binary response is also utilized in assessing suicidal behavior for the following categories: actual attempt, interrupted attempt, aborted attempt, preparatory acts or behavior, suicidal behavior, and suicide. Actual attempts are then scored based on their potential/actual lethality and/or medical damage.

The outcome of the C-SSRS is a numerical score obtained from the aforementioned categories.

8.1.10.1. *Virus Serology*

Virus serology (HIV, hepatitis B, and hepatitis C) will be assessed at the timepoints specified in the Schedule of Assessments ([Table 4](#)).

8.1.10.2. *Pregnancy Screen*

Pregnancy testing will be performed as indicated in [Table 4](#). Subjects will complete a urine pregnancy test monthly from Day 1 through the last Safety Follow-Up either at the site or at home (for months where an on-site visit is not scheduled). All pregnancy tests will be documented in the source and eCRFs.

Subjects will self-report all pregnancies through 6 months after last dose of study drug.

8.2. Adverse Events, Serious Adverse Events, and Other Safety Reporting

8.2.1. Definition of Adverse Events

An AE is any untoward medical occurrence associated with the use of a study intervention in humans, whether or not it is considered related to the study intervention. An AE can therefore be any unfavorable and unintended sign (for example, an abnormal laboratory finding), symptom, or disease in a study subject who is administered with study intervention in this study.

For this protocol, untoward medical occurrences that meet and do NOT meet the criteria of an AE include the following:

Events Meeting the AE Definition

- All AEs during the course of treatment with study intervention
- All AEs resulting from medication misuse, abuse, withdrawal, or overdose of study drug
- All AEs resulting from medication errors, such as dispensing or administration error outside of what is described in the protocol
- Apparent unrelated illnesses, including worsening of a preexisting illness
- Injury or accidents. Note that if a medical condition is known to have caused the injury or accident (a fall secondary to dizziness), the medical condition (dizziness) and the accident (fall) should be reported as 2 separate AEs. The outcome of the accident (hip fracture secondary to the fall) should be recorded in source documents.

- Abnormalities in physiological testing or physical examination findings that require clinical intervention or further investigation (beyond ordering a repeat [confirmatory] test)
- Laboratory or ECG abnormalities that require clinical intervention or further investigation (beyond ordering a repeat [confirmatory] test) unless they are associated with an already reported clinical event

Events NOT Meeting the AE Definition

- Laboratory abnormalities associated with a clinical event should be captured in the source documents. Laboratory abnormalities not requiring clinical intervention or further investigation will be captured as part of overall laboratory monitoring and should not be reported as AEs.
- The disease/disorder being studied or expected progression, signs, or symptoms of the disease/disorder being studied, unless more severe than expected for the subject's condition (see Section 8.2.10).
- Preexisting condition (eg, allergic rhinitis) must be noted on the appropriate eCRF for Screening but should not be reported as an AE unless the condition worsens, or the episodes increase in frequency during the AE reporting period.
- Diagnostic and therapeutic noninvasive and invasive procedures, such as surgery, should not be reported as AEs, unless the medical condition for which the procedure was performed meets the definition of an AE. For example, an acute appendicitis that occurs during the treatment with study intervention should be reported as the AE, and the resulting appendectomy should be recorded in the source documents and eCRF. If a surgical procedure was planned prior to entry into the study, and the surgery is not performed because of a worsening of a baseline condition, this should not be reported as an AE. Note that, as described in Section 8.2.2, any hospitalization occurring as the consequence of an AE during the study period should be reported as an SAE.

Each AE is to be classified as serious or nonserious by the investigator using medical and scientific judgment.

Treatment of AEs will be symptom-based and at the discretion of the investigator.

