8.2.2. Definition of Serious Adverse Events

An SAE is an untoward medical occurrence or effect at any dose, regardless of whether it is considered to be related to the study intervention, which results in one of the following:

- Results in death. This includes all deaths on treatment or within 6 months after last study intervention administration, including deaths due to disease progression. Any death occurring later than 6 months following the last dose need not be reported as an SAE unless it is a result of an event that started within the period covered by the on-study definition. The reported AE should be the event that caused the death.
In addition, any AE resulting in death that occurs post the AE reporting period and that the investigator assesses as possibly related to the study intervention should also be reported as serious.

- Is life-threatening. This refers to an event in which the subject was at risk of death at the time of the event. It does not include an event that, had it occurred in a more severe form, hypothetically might have caused death.
- Requires hospitalization or prolongation of existing hospitalization (excluding hospitalizations for administration of the study intervention, procedures required by the study protocol, or treatment-related diagnostic procedures; other planned hospitalizations; or hospitalizations related only to progression of disease). Emergency room visits that do not require admission to the hospital do not fall into this category, but the event may still be serious due to another seriousness criterion.
- Results in persistent or significant disability or incapacity or substantial disruption of the ability to conduct normal life functions.
- Any other medically important event that the investigator or PTC judges to be serious or which is defined as serious by the regulatory agency in the local country. These are AEs that might not be immediately life-threatening or result in death or hospitalization but might jeopardize the subject or might require intervention to prevent one of the other outcomes listed above. Medical judgment should be exercised in deciding whether an AE is serious based on the above definition. Examples of such events are intensive treatment in an emergency room or at home for allergic bronchospasm, blood dyscrasias or convulsions that do not result in hospitalization, or development of drug dependency or drug abuse.

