8.2.3. Adverse Events Reporting

Adverse events will be reported by the subject.

The investigator and any qualified designees are responsible for detecting, documenting, and recording events that meet the definition of an AE or SAE and remain responsible to pursue and obtain adequate information both to determine the outcome and to assess whether the event meets the criteria for classification as an SAE or caused the subject to discontinue the study intervention (see Section 4.4).

Each subject will be questioned about the occurrence of AEs in a nonleading manner.

In addition, the investigator may be requested by PTC Pharmacovigilance Department to obtain specific follow-up information in an expedited fashion.

All AEs are to be recorded in the source documents and on the eCRF using concise medical terminology; whenever possible, terms contained in the Medical Dictionary for Regulatory Activities (MedDRA) should be employed. In addition, the following information should be recorded:

- Indication of whether the event is serious or nonserious (see Section 8.2.2)
- Relationship to study intervention (see Section 8.2.5)
- Severity of the event (see Section 8.2.5)

- Onset date
- Resolution date, or date of death
- Action taken
- Outcome of the event

Table 6 summarizes the investigator site requirements for recording AEs on the eCRF and for reporting SAEs and adverse events of special interest on the SAE Report Form to PTC Pharmacovigilance Department.

Table 6: Investigator Site Requirements for Recording/Reporting Adverse Events

Event	Recorded on the eCRF	Reported to PTC Pharmacovigilance Within 24 Hours of Awareness
Serious AE	All	All
Nonserious AE	All	None
AESI	Not applicable	Not applicable
Other, eg, exposure during pregnancy or breastfeeding	All (regardless of whether associated with an AE)	All (regardless of whether associated with an AE)

Abbreviations: AE, adverse event; AESI, adverse event of special interest; eCRF, electronic case report form

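### Protocol 8.2.1 does not clearly require the injury from a condition-caused accident to be entered as its own AE, so its preferred term may be missing from the SAP 6.1 safety tables

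*Protocol*

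**What the plan says.** Protocol 8.2.1 puts injuries and accidents in its list of events that meet the AE definition. The bullet begins "Injury or accidents. Note that if a medical condition is known to have caused the injury or accident (a fall secondary to dizziness", and goes on to say that "the medical condition (dizziness) and the accident (fall) should be reported as 2 separate AEs". The next sentence deals with the injury itself: "The outcome of the accident (hip fracture secondary to the fall) should be recorded in source documents".

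Later in 8.2.1, in the appendicitis example, "the resulting appendectomy should be recorded in the source documents and eCRF". The same section adds that "any hospitalization occurring as the consequence of an AE during the study period should be reported as an SAE".

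Protocol 8.2.2 opens with "An SAE is an untoward medical occurrence or effect at any dose" and makes no exception for an injury that follows an accident. Protocol 8.2.3 states: "All AEs are to be recorded in the source documents and on the eCRF".

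SAP 6.1 summarizes TEAEs and TESAEs by system organ class and preferred term, with further tables by maximum severity and by relationship to treatment. Its listings cover AEs, deaths, SAEs and discontinuations.

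**The concern.** A fracture, head injury or bleed after a fall is an untoward medical event in its own right. If it is written only in the source documents, it is never coded, and no table or listing built from AE records can show it under its own name.

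Safety against placebo is a primary objective of this study. Protocol 7.2.4 links gait changes to decline in Huntington's disease, and the study measures gait, balance and postural sway, so falls are a foreseeable event here. Protocol 8.2.12 defines no adverse events of special interest, so there is no second route by which injuries would be collected. A record of a serious grade 3 fall tells the reader that something bad happened, but not what the injury was.

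**Working it through.** The point rests on wording, so no formula applies. The check is to follow the protocol's own example through the recording rules and into the tables, assuming onset within the treatment-emergent window and a hospital admission.

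| Element | What 8.2.1 asks for | What SAP 6.1 would show |
|---|---|---|
| Dizziness | AE | TEAE under its own preferred term |
| Fall | AE | TEAE under its own preferred term; TESAE because of the admission |
| Hip fracture | Source documents; eCRF not named | No preferred term of its own, if the text is followed literally |

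Three medical facts give two AE records, so 3 − 2 = 1 term has no record.

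**Is the literal reading reasonable?** Three features of the text support it.

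1. The number of AEs is fixed at two. Entering the fracture would make three.
2. Where the authors want the eCRF, they usually name it, as in the appendectomy example in 8.2.1 and the general rule in 8.2.3.
3. In the list of events that do not meet the AE definition, 8.2.1 sends laboratory abnormalities tied to a clinical event to source documents in almost the same words. There the phrase describes something that is not reported as an AE.

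**Where does it conflict with other text?**

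1. The same bullet in 8.2.1 lists injuries as events that meet the AE definition.
2. Under 8.2.2, when a subject dies, the AE to report is the one that caused the death. If a fall after dizziness leads to a fatal head injury, 8.2.2 points to the head injury, while 8.2.1 sends it to source documents.
3. Under 8.2.3, every AE goes on the eCRF. If the fracture is an AE by the bullet's own heading, it belongs there.
4. Under 8.2.4.1, the SAE form and the AE page must agree and use the same term. A site that names the fracture on the SAE form would have no matching eCRF entry under the literal rule in 8.2.1.

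**What is kept?** Dizziness and fall each have a record with severity, seriousness and causality. Protocol 8.2.5.1 asks for the highest grade reached in each episode, so the fall can carry the severity of what followed. Hospitalization makes the event an SAE. The loss is limited to the identity and count of the injury.

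**The case against.** The strongest reply is that the text never says source documents alone. It does not forbid an AE entry, and the contrast with the appendectomy example is an inference. Protocol 8.2.13 supports this reply: it says medication errors are recorded in source documents, while Table 9 in the same section requires all of them on the eCRF. Other rules may also reach the injury. Examination findings that need intervention are AEs under 8.2.1, and the SAE definition is broad. This reply stands to the extent that exclusion from the eCRF is a likely reading, not a certain one. It does not remove the problem, because sites can read the rule either way and record the same injury differently.

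Three stronger readings are tempting, and the documents do not support them.

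- **These injuries vanish from the safety tables altogether.** The condition and the fall are tabulated, and the fall becomes a TESAE if the subject is admitted. Only the injury's own term is at risk.
- **These are the injuries most likely to be drug-related.** The rule covers any causal condition, including Huntington's disease itself or an intercurrent illness. A suspected drug effect such as dizziness is itself reported.
- **The comparison between arms is biased toward no harm.** The rule is the same in every arm of a double-blind study. If the drug did raise condition-caused falls, more injury terms could go uncounted on active treatment, but the excess of dizziness and falls would still appear. The SAP plans no separate comparison of injuries.

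It can also be argued that the source-documents sentence covers the outcome of any accident, not only one caused by a condition. That would remove the uneven treatment of two identical fractures, but it would widen the recording gap.

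**Conclusion.** The point holds as an inconsistency in the recording rule with a limited effect on reporting. Followed literally, Protocol 8.2.1 leaves the resulting injury without a preferred term in the SAP 6.1 TEAE and TESAE tables, although its cause and the accident are counted. Injury types then cannot be told apart, and their counts can be understated.

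The size is up to one preferred term for each distinct injury that is not entered. The documents give no rate of falls or injuries, so no number of subjects per arm can be stated. Nor can different injuries be added together against the SAP's 5% table, because that table works by single preferred term.

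The conclusion assumes that sites take the sentence at face value and that no eCRF completion instruction outside these documents says otherwise. The change is worth making because it is cheap and serves a primary safety objective.

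**What to change.** Reconcile Protocol 8.2.1 with 8.2.2, 8.2.3 and 8.2.4.1 by replacing the sentence on the outcome of the accident. Suggested text: *Each clinically significant injury resulting from the accident (such as a hip fracture) is also recorded as a separate AE on the eCRF, with its own severity, seriousness and causality.* An eCRF completion instruction with the same content would also serve.

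For subjects already enrolled, ask sites to enter such injuries from source documents before the database lock for the double-blind treatment period. The rule already sends these details to source documents, so the information should be available. SAP 6.1 needs no change, because the new records would flow into its existing tables and listings.

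The cost is one sentence and a few back-entered rows. The downside is that one accident can add a third preferred term, so AE counts rise slightly in all arms.
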